#### 8.4. Data sources

The Swedish administrative registries offer high quality data for research with nation-wide coverage and close to complete data for most available variables. Patient-level data from each register is available for research purposes and individual patients can be linked between all data sets via the personal identifier given to all citizens. The administrative registers to be used in this study are summarized in Table 2.

**Table 2. Overview of data sources**

Type of register	Name	Data holder	Start of data collection	Variables
Patient register	Swedish National Patient Register	NBHW	1987/2001	Diagnosis codes (ICD-9/10), dates, procedure codes and types of visit
Prescription register	Swedish Prescribed Drug Register	NBHW	2005	Dispatch dates, type of medication (ATC codes), strengths and dosages
Information on mortality	Swedish Causes of Death Register	NBHW	1961	Date and cause of death (ICD-10)
Cancer register	Swedish Cancer Register	NBHW	1958	Morphological diagnosis of the tumour (ICD-O/3)

The individual data will be extracted from the PDR and merged with the data from the SCR and the NPR using the personal identification numbers (PINs). The data extraction will cover all patients aged  $\geq 18$  years with at least one filled prescription of an oral targeted therapy relevant for treating mRCC registered in the Swedish Prescribed Drug Register between 01 July 2005 (there is no data available in the register before this date) and 31 December 2019. The Anatomical Therapeutic Chemical (ATC) codes for the oral drugs relevant for treating mRCC are the following: L01XE04 (sunitinib), L01XE05 (sorafenib), L01XE11 (pazopanib), L01XE17 (axitinib), L01XE10 (everolimus), L01XE26 (cabozantinib), L01XE34 (tivozanib), L01XE29 (lenvatinib).

PFIZER CONFIDENTIAL

The PDR does not provide any information on mRCC, which is the area of interest in this study. The analysis therefore combines the PDR, the SCR and the NPR with the aim to identify the mRCC cohort. The patients identified in the PDR that also are identified in the SCR with the International Classification of Diseases and Related Health Problems (ICD)-7 diagnosis codes I800 or I809 and ICD-10 codes C64.0 and C64.9 from 01 January 2000 until 31 December 2019; excluding ICD-7 code I801 (cancer of the renal pelvis) will be included in the analysis set.

The two analysis sets described in Section 8.2 will be derived and used in the analyses.

### **8.5. Study size**

An estimated 17,000 to 18,000 patients are diagnosed with RCC between 01 January 2000 and 31 December 2019, approximately 1,000 patients per year. Of these patients, an estimated 4,000 to 5,000 are registered with at least one relevant dispensed prescription for mRCC. Approximately 1,000 of these patients are estimated to have received sunitinib as first line treatment during the investigated period. For axitinib, approximately 300 patients are estimated to have received it in second line during the investigated period.

### **8.6. Data management**

In broad terms, the data management for this study will be initiated by the creation of a broad study population including patients with at least one filled prescription of (L01XE04 (sunitinib), L01XE05 (sorafenib), L01XE11 (pazopanib), L01XE17 (axitinib), L01XE10 (everolimus), L01XE26 (cabozantinib), L01XE34 (tivozanib), L01XE29 (lenvatinib)) identified in the PDR. A study key including the selected cases personal identifiable number (PIN) and a randomly created study identification number will be created by the NBHW. The data that is being extracted from the NBHW is described in Table 3 below.

PFIZER CONFIDENTIAL

Based on the data extracted from the NBHW two completely pseudonymized analytical dataset comprising all observations and variables required for the planned analyses will be compiled, see details in Section 8.2. The analytic datasets will be person-level.

[figure not shown]
All data management will be performed by ICON. A data validity quality check is always undertaken before data management is started to verify that all variables are complete and to create logs for corrupt or ambiguous data entries. Data will be analyzed using SAS version 9.2 or later.

One of the variables included in the material (DOSER) is in text format, requiring human review. The information in DOSER will be reviewed for Analysis Set 1 (patients identified with sunitinib treatment in first line) and used to identify the initial dosing schedule and changes in the dosing schedule. The information in DOSER will be quantified in the following way. DOSER will be lifted out to an excel sheet together with study IDs and drug dispense dates. DOSER will be manually reviewed and dummy variables indicating the dosing schedule and dates for changes in the dosing schedule will be created. When the manual coding is done, the data will be merged with the original dataset based on the study IDs.

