## 8. RESEARCH METHODS

### 8.1. Study design

To address the research objectives, the study will be carried out as a national retrospective population-based register study based on data from the NBHW.

Based on the study objectives, the primary endpoint in this study is:

- Time to treatment discontinuation in first line sunitinib patients. Time to event measure from index date to discontinuation of treatment, from 01 July 2005 to 31 December 2019 (assessed from index date up to 180 months). This will be investigated using Kaplan-Meier analysis.

[figure not shown]

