### Time to treatment discontinuation

Time to treatment discontinuation, or persistence, is defined as the difference between the start and end-dates for a treatment episode (accordance with the International Society for Pharmacoeconomics and Outcomes Research (ISPOR) Medication Compliance and Persistence Work Group) regardless of reason for discontinuation. The start date for a treatment episode is defined as the date of first dispensed package and the end date is defined as the date of the last dispensed package with the same ATC code, plus the number of days that package, as well as accumulated medicine (see more details below), is intended to cover. This end date is overruled if there is a new filled prescription of another relevant ATC code or death happens before this, then either of these dates represents the end date. If no end of prescribed supply is recorded, data is censored at latest available date in data.

[figure not shown]
Time to treatment discontinuation will be calculated while allowing for patient accumulation of medicine. The number of days covered by the dispensed volume will be determined based on information in the Summary of Product Characteristics (SPC), the volume of dispensed drug, and for sunitinib in first line also by using the prescriber's dosing instruction on the prescription available in the PDR.

For sunitinib, the treatment is provided in 4 + 2 (or 2 + 1) week cycles, where there is a two-week break in treatment after four weeks of continuous drug intake. Hence, the assumed number of days covered by each filled prescription will be adjusted accordingly (i.e. the 14 or 7 days corresponding to the cycle will be added).

When previously supplied dosing instructions cease to be specified, it is assumed that the daily dosage continues in accordance with the previous treatment pattern. Should there be a completeness issue with the variable containing dose information; the recommended average dose per day according to the SPC for each product will be used instead.

[figure not shown]
For axitinib, the treatment is provided in 4 week cycles, without breaks in between. The analysis relies on data on information relating to dispensed pack size and strength;

PFIZER CONFIDENTIAL

Axitinib is available in pack size of 56 tablets, and in strength 1, 3, 5 and 7 mg. Given the dosing recommendations in SPC, a dispensed pack with the strength 1 mg is assumed to last 14 days, whereas the other packs are assumed to last 28 days.

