## **Dosing Schedule**

The different treatment schedules for sunitinib that will be analysed (starting on 4:2, starting on 2:1 and starting on 4:2 and then switching to 2:1) will be defined based on the dosing instruction provided by the prescriber and will be reviewed manually (the variable DOSER in the Swedish Prescribed Drug Register). In the case no instruction is provided at the start of the treatment, a 4:2 dosing scheme (recommended dose in the SPC) will be assumed. When previously supplied dosing instructions cease to be specified, it is assumed that the daily dosage continues in accordance with the previous treatment pattern. A patient is defined as having switched from a 4:2 to a 2:1 schedule if the dosing instruction clearly indicates this. Other sunitinib dosing schedules than the ones described above will not be included in the analysis but will be included in descriptive statistics.

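### Sunitinib schedule is hand-coded in a sheet that also shows dispensing dates, so exposure is judged with a close proxy for time to discontinuation in view

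*Combined protocol and SAP*

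**What the plan says.** **Coding.** Section 8.6 (Data management) covers the free-text dosing variable in Analysis Set 1: "DOSER will be lifted out to an excel sheet together with study IDs and drug dispense dates". It continues: "DOSER will be manually reviewed and dummy variables indicating the dosing schedule and dates for changes in the dosing schedule will be created". The codes are then merged back on study ID.

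**Rules for the coder.** Dosing Schedule (Section 8.2.1) says: "A patient is defined as having switched from a 4:2 to a 2:1 schedule if the dosing instruction clearly indicates this". If there is no instruction at the start, "a 4:2 dosing scheme (recommended dose in the SPC) will be assumed". If instructions lapse, the previous pattern is carried forward. Other schedules are described but left out of the analysis.

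**Endpoint.** Section 8.1 names the primary endpoint as "Time to treatment discontinuation in first line sunitinib patients". Section 8.2.1 fixes its beginning: "The start date for a treatment episode is defined as the date of first dispensed package". It ends at the last dispensing plus the days that pack and any accumulated supply cover, or earlier at another relevant drug or death. A gap of more than 90 days ends persistence.

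**Use.** The coded groups are the three columns of Table 4. Section 8.7 plans log-rank tests across cohorts and Cox models.

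**The concern.** Whether a text meets the test "if the dosing instruction clearly indicates this" is a judgement, and the plan gives no further criteria for it. The coder makes that judgement with study ID and dispense dates alongside. Even without dates, the number of rows per study ID tracks time on drug.

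The background in Section 6 describes a retrospective study of 249 patients that found longer drug survival after a move to 2:1. A coder acting in good faith may therefore expect long treatment to go with a switch. If unclear texts are resolved differently for long- and short-treated patients, exposure is misclassified in a way that depends on the outcome. This would distort medians and curves as well as tests, so the study's descriptive label does not remove the problem. Nor can adjustment for age, gender, year and region repair it.

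The dates are needed to date a switch. They are not needed to read the text.

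**Working it through.** The plan gives no error rate or share of unclear texts, so there is no figure of its own to reproduce. The check has three parts.

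**1. What the sheet shows against what the endpoint needs**

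| Component of the endpoint (Section 8.2.1) | Listed for the coding sheet (Section 8.6)? |
|---|---|
| First dispense date | Yes |
| Last dispense date | Yes |
| Gaps between dispensings | Yes, from the dates, apart from pack coverage |
| Days covered by packs, accumulated supply | Not listed |
| Fill of another relevant drug | Not listed |
| Death | Not listed |

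That every sunitinib dispensing is in the sheet is an inference, but a safe one, because changes of schedule cannot be found and dated without them. The coder sees most of the duration but not the exact endpoint.

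**2. Is the coding masked or checked?** The validity check in Section 8.6 logs ambiguous entries, but it takes place before data management starts. Quality control in Section 8.8 concerns the extraction from the data holder. No section states masking, written coding criteria, a second coder or an agreement check. Section 10 also contains a general paragraph saying that text is converted by computer only. This conflicts with the human review described in Sections 8.2.1, 8.6 and 9.1 and later in Section 10 itself.

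**3. Possible size, illustration only**

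The one input from the plan is about 1,000 first-line sunitinib patients (Section 8.5). Everything else is assumed: no true difference, exponential durations, no censoring, 30% clear switchers, and 5% to 30% of patients with an unclear text. Unclear texts are coded as a switch with probability pL if duration is above the median and pS if below.

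By hand, with 10% unclear, pL = 0.6 and pS = 0.2:
- Clear patients: 900, of whom 0.3 × 900 = 270 are switchers (135 long) and 630 are not (315 long).
- Unclear patients: 50 long give 0.6 × 50 = 30 coded as switch; 50 short give 0.2 × 50 = 10.
- Long-treated share, coded switch: (135 + 30) / (270 + 40) = 165/310 = 53.2%.
- Long-treated share, coded no switch: (315 + 20) / (630 + 60) = 335/690 = 48.6%.

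The difference comes from the coding alone. Simulation with 400 replicates per setting gives the apparent hazard ratio for discontinuation (switch against no switch) and the false-positive rate of a two-sided 5% log-rank test:

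| Unclear | None (0.3/0.3) | Mild (0.5/0.3) | Moderate (0.6/0.2) | Strong (0.8/0.1) |
|---|---|---|---|---|
| 5% | 0.99, 4.8% | 0.99, 5.0% | 0.97, 7.0% | 0.94, 12.8% |
| 10% | 1.00, 5.2% | 0.98, 5.8% | 0.94, 14.2% | 0.89, 38.0% |
| 20% | 1.00, 6.0% | 0.94, 14.8% | 0.89, 42.0% | 0.81, 91.5% |
| 30% | 1.00, 4.5% | 0.91, 29.0% | 0.83, 79.5% | 0.73, 100% |

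The simulation error on a 5% rate is about √(0.05 × 0.95 / 400) = 1.1 percentage points. Few unclear texts with mild dependence do almost nothing; many with strong dependence do a great deal.

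**The case against.** **The defaults limit discretion.** A missing starting instruction means 4:2, lapsed instructions carry forward, and a switch counts only if clear. Applied strictly, an unclear text is never a switch, whatever the duration; in the table's terms that is equal probabilities and no bias. This stands as a limit, but what counts as clear, and what counts as another schedule, is still decided by the coder with the dates in view.

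**The coder does not see the outcome.** A reader might infer that the coder sees the primary endpoint itself. The documents do not support that: pack coverage, other drugs and death are not listed for the sheet.

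**Nothing shows that bias occurs.** A reader might also infer that a large part of the 2:1 or switch groups rests on outcome-aware judgement. The documents give neither the size of those groups nor the share of unclear texts, so this cannot be claimed. The coding probabilities in the simulation are assumptions too.

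**Masking is not a full cure.** Patients treated longer have more texts and so more chances of a false switch, even with a masked coder. At an assumed 2% per independent text, the chance is 1 − 0.98^4 = 7.8% with 4 texts and 1 − 0.98^20 = 33.2% with 20. Coding each unique string once helps where texts repeat, but the number of distinct texts is still likely to grow with time on drug. This objection stands.

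**The coding may already be done.** Data collection was planned to end on 31 March 2021 (Section 5) and this version is dated 13 April 2021. The reason given for amendment 1 in Section 4, that too many switchers were lost with a 30-day gap, suggests that switches had been identified at least once. This affects the cost of a change, not the point.

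**Conclusion.** The concern holds as an opportunity for outcome-dependent misclassification of schedule in the Table 4 comparison. The coder has a close proxy for time to discontinuation in view, some judgement remains after the defaults, and no safeguard is stated. The size is unknown. In the illustration the apparent hazard ratio runs from 0.99 (5% unclear, mild dependence) to 0.73 (30% unclear, strong dependence), and it stays at 0.99 to 1.00 when coding does not depend on duration. All of this rests on assumed shares and assumed coder behaviour.

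The documents do not support saying that the results are biased, or that the analysis is invalid. The change is worth making because it is a cheap improvement on the stated procedure. That a switcher must stay on drug long enough to switch is a separate issue and is not counted here.

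**What to change.** 1. Export the unique dosing texts with a string key only, without study ID or dispense date. Code each once as 4:2, 2:1, other or unclear, and merge back on the key.
2. Derive starting schedule, carry-forward under the Dosing Schedule rules, and switch date by program from the dispense date (EDATE, Table 3).
3. Give unclear strings a second look with only the preceding instruction shown. Apply the Dosing Schedule defaults to those still unclear, report how many there are, and add a sensitivity analysis that excludes those patients.
4. Let someone other than the coder hold the link from key to study ID, so that an adverse event found in a text can be re-linked and reported within the 24 hours, and with the patient identifier, that Section 10 requires.
5. If coding has already been done, re-code the unique strings masked and report agreement with the existing codes.
6. Reconcile the computer-only paragraph in Section 10 with the manual review.

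**Cost.** No new data are needed, and repeated texts are read once. The downsides are the re-linking step, the second look and a possible re-code, ideally by someone who has not seen the dates. The greater chance of a false switch in patients with more dispensings remains and should be stated in Section 8.9.

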**Table 3. Variables extracted from the NBHW**

Variable	Explanation	Data source(s)
ICD7	ICD-7 code	Swedish Cancer Register
ICD9	ICD-9 code	Swedish Cancer Register
ICDO10	ICD-O/2-10	Swedish Cancer Register
ICDO3	ICD-O/3	Swedish Cancer Register
ALDER	Age at diagnosis	Swedish Cancer Register
M	Spread of tumor at diagnosis, distant metastases	Swedish Cancer Register
N	Spread of tumor at diagnosis, Lymph nodes	Swedish Cancer Register
DIADAT	Date of RCC diagnosis	Swedish Cancer Register
DODSDAT	Date of death	Swedish Cancer Register
DODSDATN	Date of death numeric	Swedish Cancer Register
KON	Gender	Swedish Cancer Register
SJUKHUS	Hospital where diagnosis was set	Swedish Cancer Register
DODSDAT	Date of death	Swedish Cause of Death Register
ALDER	Age at visit	National Patient Register
AR	Year of visit	National Patient Register
MVO	Medical focus area	National Patient Register
SJUKHUS	Hospital	National Patient Register
DIAGNOS	Diagnosis	National Patient Register
HDIA	Main diagnosis	National Patient Register
KON	Sex	National Patient Register

PFIZER CONFIDENTIAL

INDATUMA	Date for start of visit	National Patient Register
OP	Surgery	National Patient Register
UTDATUMA	Date for end of visit	National Patient Register
VTID	Duration of care	National Patient Register
ALDER	Age at the end of the year	Swedish Prescribed Drug Register
ARBLAN	The region of the prescribing clinic	Swedish Prescribed Drug Register
FDATE	Prescription date	Swedish Prescribed Drug Register
EDATE	Dispense date	Swedish Prescribed Drug Register
ANTAL	Number of packages	Swedish Prescribed Drug Register
DOSER	Dosing instructions	Swedish Prescribed Drug Register
EXPLAN	Region/County of dispensing pharmacy	Swedish Prescribed Drug Register
FVARUNR	Dispensed drug goods number	Swedish Prescribed Drug Register
ATC	ATC code	Swedish Prescribed Drug Register
PRODUKT	Name of product	Swedish Prescribed Drug Register
FORPS	Package size	Swedish Prescribed Drug Register
STYRKALF	Strength of the product	Swedish Prescribed Drug Register
STYRKAENHET	Unit of the strength	Swedish Prescribed Drug Register
KON	Gender	Swedish Prescribed Drug Register

#### **8.6.1. Case report forms (CRFs)/Data collection tools (DCTs)/Electronic data record**

As used in this protocol, the term DCT should be understood to refer to either a paper form or an electronic data record or both, depending on the data collection method used in this study.

A DCT is required and should be completed for each included patient. The completed original DCTs are the sole property of Pfizer and should not be made available in any form to third parties, except for authorized representatives of Pfizer or appropriate regulatory authorities, without written permission from Pfizer. ICON shall ensure that the DCTs are securely stored at the study site in encrypted electronic form and will be password protected to prevent access by unauthorized third parties.

ICON has ultimate responsibility for the collection and reporting of all clinical, safety, and laboratory data entered on the DCTs and any other data collection forms (source documents) and ensuring that they are accurate, authentic/original, attributable, complete, consistent, legible, timely (contemporaneous), enduring, and available when required. The DCTs must be signed by ICON staff or by an authorized staff member to attest that the data contained on the DCTs are true. Any corrections to entries made in the DCTs or source documents must be dated, initialed, and explained (if necessary) and should not obscure the original entry.

PFIZER CONFIDENTIAL

The source documents are the hospital or the physician's chart. In these cases, data collected on the DCTs must match those charts.

### **8.6.2. Record retention**

To enable evaluations and/or inspections/audits from regulatory authorities or Pfizer, ICON agrees to keep all study-related records, including the identity of all participating patients (sufficient information to link records, e.g., CRFs and hospital records), copies of all DCTs, safety reporting forms, source documents, detailed records of treatment disposition, and adequate documentation of relevant correspondence (e.g., letters, meeting minutes, and telephone call reports). The records should be retained by ICON according to local regulations or as specified in the vendor contract, whichever is longer. ICON must ensure that the records continue to be stored securely for so long as they are retained.

If ICON becomes unable for any reason to continue to retain study records for the required period, Pfizer should be prospectively notified. The study records must be transferred to a designee acceptable to Pfizer.

Study records must be kept for a minimum of 15 years after completion or discontinuation of the study, unless ICON and Pfizer have expressly agreed to a different period of retention via a separate written agreement. Record must be retained for longer than 15 years if required by applicable local regulations.

ICON must obtain Pfizer's written permission before disposing of any records, even if retention requirements have been met.

### **8.7. Data analysis**

An overview of the planned analyses are presented in this section. In general, the study is descriptive and does not involve hypothesis testing. Any major modifications of primary endpoint definitions or their analyses would be reflected in a protocol amendment.

Time-to-event analyses will be carried out using standard Kaplan-Meier methods. Kaplan-Meier survival functions will be estimated with relevant events as failure. Time-to-event tables

PFIZER CONFIDENTIAL

and Kaplan-Meier curves will be presented. Log-Rank tests will be used to assess differences across cohorts. In addition, to explore potential determinants of persistence /drug survival and to adjust for differences across cohorts, semi-parametric cox-proportional hazard models will be deployed based on different covariates.

Relevant events for this study include:

- Time to treatment discontinuation
- Death

Time-to-event tables will present:

- Failed/Censored n (%).
- Median time to event.
- 95% confidence intervals of median.
- The 25th and 75th percentiles (q1 and q3).
- Min and max.
- n at risk by unit.
- Time point estimates and 95% Confidence Intervals (CI)by unit.

[figure not shown]
As described in Section 8.2 the analyses will be carried out based on two analysis sets.

Analysis Set 1 consists of all patients indentified with sunitinib as the first line treatment.

Analysis Set 2 consists of all patients indentified with axitinib as the second line treatment.

The Table 4 below displays the output from the time to treatment discontinuation and overall survival analyses that will be carried out based on Analysis Set 1. The output will be presented for three different dosing schemes of interest, patients that started on a 4:2 schedule and that did not switch, patients that started on a 4:2 schedule but later switched to a 2:1 schedule and patients that started on a 2:1 schedule and did not switch. Output will also be presented as Kaplan Meier (KM) curves.

PFIZER CONFIDENTIAL

[figure not shown]

To explore potential determinants drug survival and to adjust for differences across cohorts, semi-parametric cox-proportional hazard models will be deployed based on the following covariates: age, gender, year of treatment initiation, region.

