Patients will be allowed to have gaps between filled prescriptions, but once such a gap exceeds 90 days (the “grace period”) they will be defined as non-persistent. As the Swedish pharmacy system allows patients to refill prescriptions when two-thirds of the previous refill has been consumed (e.g. after two months of a three-month prescription) patients may accumulate large amounts of medication. To account for that, patients will be permitted to accumulate medication from overlapping prescriptions and use it to cover future gaps between filled prescriptions. Figure 1 depicts the effect the grace period and accumulation of medication may have on persistence with the help of scenario 1 and 2.

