## Overall survival

Overall survival is defined as the time (number of days) from the start of the treatment (the date of the first dispensed package, of sunitinib or axitinib) until the date of death as documented in the Cause of Death Register. If no death is recorded, data is censored at latest available date in data.

[figure not shown]

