**Table 1. Overview of study variables**

Variable	Role	Data source(s)	Operational definition
Total number of sunitinib 1L patients	Outcome	Prescription Register	Number of sunitinib users with at least one filled prescription (in total and per year over time)
Number of sunitinib 1L 4:2 schedule users	Outcome	Prescription Register	Number of sunitinib users that started on a 4:2 schedule and never had a modification in the schedule (total and per year over time)
Number of sunitinib 1L 2:1 schedule users	Outcome	Prescription Register	Number of sunitinib users that started on a 2:1 schedule and never had a modification in the schedule (total and per year over time)
Number of sunitinib 1L patients that was switched from a 4:2 schedule to a 2:1 schedule	Outcome	Prescription Register	Number of sunitinib users that started on a 4:2 schedule and later was switched to a 2:1 schedule, in total and per year over time

PFIZER CONFIDENTIAL

Total number of axitinib second line patients	Outcome	Prescription Register	Number of axitinib 2L users with at least one filled prescription (in total and per year over time)
Gender	Baseline characteristics	Prescription Register	Male/Female (binary)
Age	Baseline characteristics	Prescription Register	Age will be defined as age at the date of first filled prescription of relevant mRCC medication (continuous; years).
Year of treatment initiation	Baseline characteristics	Prescription Register	Defines the year the treatment was initiated.
Region	Baseline characteristics	Prescription Register	County council of the prescribing physician at first prescription date (categorical), see Table 6 in Annex 3
Time to treatment discontinuation	Outcome	Prescription Register	Time from date of first filled prescription to the end of the prescribed supply, or prescription of other ATC code or death if either of these happen before (details in Section 8.2).
Overall survival	Outcome	Cause of Death Register, Prescription Register	Time from date of first filled prescription of the relevant drug to date of death (number of days) where death is defined as all-cause death; If no date of death is recorded, data is censored at latest available date in data.

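### Sunitinib switchers and non-switchers are compared from first dispensing although switching is known only later, so the switch comparison contains immortal time

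*Combined protocol and SAP*

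**What the plan says.** **Time zero.** For TTD, section 8.2.1 states "The start date for a treatment episode is defined as the date of first dispensed package". OS runs "from the start of the treatment (the date of the first dispensed package, of sunitinib or axitinib) until the date of death". Both clocks start at the first fill.

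**Cohorts.** Table 1 counts "Number of sunitinib users that started on a 4:2 schedule and never had a modification in the schedule" and, separately, "Number of sunitinib users that started on a 4:2 schedule and later was switched to a 2:1 schedule". The evidence for a switch is a later prescription: "A patient is defined as having switched from a 4:2 to a 2:1 schedule if the dosing instruction clearly indicates this". No time window is given, and the text does not say that the switch must fall in the first treatment episode. A first episode ends once a gap exceeds 90 days, when patients have stopped by definition ("they will be defined as non-persistent"). A missing first instruction is handled by default: "In the case no instruction is provided at the start of the treatment, a 4:2 dosing scheme" is assumed.

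**Analysis.** Section 8.7 and Table 4 show the three schedule groups side by side, among them "patients that started on a 4:2 schedule but later switched to a 2:1 schedule", with Kaplan-Meier estimates, log-rank tests for differences between cohorts, and Cox models. The listed covariates are age, gender, year of initiation and region. How schedule enters the Cox models is not stated. The only stated sensitivity analysis varies the grace period (60 and 120 days). Section 8.9 mentions selection and misclassification bias in general terms, but not immortal time or confounding by the reason for switching.

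**An inconsistency.** Table 1 and the text of section 8.7 restrict the 2:1 cohort to patients whose schedule never changed. The Table 4 column for 2:1 carries no such restriction, although its 4:2 counterpart does.

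**The concern.** A 4:2 starter who dies before any change of schedule can only be a non-switcher. A switcher has, by definition, survived to the switch. The time between first fill and switch is therefore event-free for OS in the switch cohort. It is also event-free for TTD when the switch falls within the first persistent episode. If switching is unrelated to prognosis, switchers will look better even when schedule makes no difference.

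Section 7 makes TTD by schedule the primary objective and OS by schedule a secondary one. Section 6 asks how these outcomes depend on schedule, and cites a retrospective study of 249 patients in which those who moved to 2:1 had longer drug survival. The planned analysis can produce that same ordering with no schedule effect. The baseline covariates cannot correct this, because the fault lies in when group membership is decided.

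**Working it through.** The plan gives no effect size, switch share, switch timing or TTD median, so there is no figure to reproduce. The check asks what the planned grouping returns when schedule has no effect.

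**Inputs.** From the documents: about 1,000 first-line sunitinib patients (section 8.5); survival of over 2 years (section 6); follow-up from 1 July 2005 to 31 December 2019, which is 14.5 × 12 = 174 months (section 8.1 prints 180). Assumed: 900 4:2 starters, median TTD 9 months, median OS 26 months, about 25% switching within the first episode, exponential times, uniform censoring over 174 months, a fixed cohort term in the Cox model, and a two-sided 5% test (section 8.7 states no alpha).

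**Closed form, constant switch rate, no censoring.**
- Stopping rate λ = ln 2 / 9 = 0.0770 per month.
- Switch rate s with s/(s + λ) = 0.25, so s = λ/3 = 0.0257.
- Non-switchers (stop before switch): exponential with rate λ + s = 0.1027; median 0.6931/0.1027 = 6.75 months.
- Switchers: waiting time at rate λ + s, then a further stay at rate λ. Survival is 4·exp(−λt) − 3·exp(−4λt/3), which equals 0.5 at t = 19.0 months.

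The medians are thus 19.0 versus 6.75 months with identical treatment. Simulation with censoring gave 18.7 versus 6.9.

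**Simulation under the null, switch versus 4:2 no switch** (ranges cover repeat runs and, for OS, two ways of linking death to stopping):

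| Switches fall within | TTD HR | OS HR | TTD log-rank rejection |
|---|---|---|---|
| 1.5 months | 0.92–0.94 | 0.96–0.97 | 14–19% |
| 3 months | 0.86–0.87 | 0.92–0.94 | 44–49% |
| 6 months | 0.75–0.77 | 0.86–0.88 | 94–97% |
| 12 months | 0.61–0.65 | 0.75–0.80 | 100% |
| constant rate | 0.40 | 0.58–0.69 | 100% |

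A separate simulation with other assumptions (1,000 patients, median TTD 6–12 months, median OS 24 months, constant switch rates giving 11–66% switching) gave TTD HR 0.20–0.46 and OS HR 0.54–0.77.

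**Prognosis-related switching.** If poor-prognosis patients switch more, the planned TTD HR was 1.23–1.24 for switches within 1.5 months and 0.74 within 12 months. If good-prognosis patients switch more, it was 0.44–0.66.

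**2:1 versus 4:2** (1,000 starters, 20% on 2:1). If no 2:1 starter ever changes and both cohorts are never-modified, the null TTD HR over the same five timings is 0.98 / 0.96 / 0.93 / 0.87 / 0.76–0.77. If 2:1 starters change as often as 4:2 starters, it is about 1.00. By starting schedule with everyone kept, TTD is 1.00 and OS 0.99–1.01.

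**Candidate remedies under the null.**
- Landmarks at 3 and 6 months among patients still on sunitinib gave 1.00–1.07 (TTD) and 0.99–1.04 (OS).
- A time-dependent switch term gave TTD HR 1.00–1.02 with continuous times. In the registers a switch is dated at a fill, and TTD is last fill plus supply, so a switcher has a full supply guaranteed just after switching. With that structure (42-day supply, refills 0–14 days early plus a random delay, 5–10% switching per fill), it gave 0.74–0.81 with no delay, 0.86–0.92 with a mean delay of 10 days and 0.92–1.00 with 20–40 days. A second run gave 0.71–0.97. Landmarks gave 0.98–1.07 with the same structure.
- A time-dependent OS model gave 0.74–0.96 when survival is TTD plus post-treatment time and patients who had stopped stayed as comparators. It gave 0.99–1.01 with comparators restricted to those on sunitinib.

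**Landmark attrition.** At 3 months: 900 × 2^(−3/9) × 171/174 = 702. At 6 months: 900 × 2^(−6/9) × 168/174 = 547.

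**The case against.** The strongest defence is that section 8.7 calls the study descriptive and without hypothesis testing, and that section 7 only undertakes to investigate outcomes for the schedules. This does not remove the problem. The Kaplan-Meier medians are themselves distorted, and the same section plans log-rank tests and adjustment across cohorts.

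Three limits do stand.

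- **Reach.** A reader might infer that the whole primary objective is compromised. The documents do not support that. Section 8.1 defines the primary endpoint as TTD in first-line sunitinib patients, and whole-cohort TTD involves no later classification. Comparing 2:1 with 4:2 is distorted only if both cohorts are restricted to never-modified patients and the two groups change schedule at different rates. The first condition is unsettled, because Table 4 conflicts with Table 1 and section 8.7; the second is unknown.
- **Restarts.** A reader might also infer that someone who stops and later restarts on 2:1 counts as a switcher. The reason given in section 4 for the 90-day grace period, that too many switchers were lost at 30 days, suggests that a switch is meant to fall within the persistent episode. The definition should say so.
- **Cox models.** Section 8.7 does not list schedule as a covariate, so bias in the Cox results is conditional on a fixed cohort term being used.

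**Conclusion.** The point holds for the contrast between 4:2 starters who switched and those who did not. For OS the event-free period is a matter of logic; for TTD it follows when switches fall in the first episode, which appears intended but is not written.

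With switching unrelated to prognosis, the bias favours switchers. The illustrative null TTD HR of about 0.93 to 0.6, and 0.40 at a constant rate, rests on a 9-month median and about 25% switching, neither of which is in the documents. If nearly all switches came within six weeks the bias would be small, but the plan sets no such limit. With prognosis-related switching the net direction is not fixed, which leaves the planned contrast uninterpretable.

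It would be too strong to say that a time-dependent covariate, or any single change, removes immortal time here. Fill-based dating leaves a residual bias for TTD. Landmarks deal only with switches made before the landmark, and confounding remains: with prognosis-related switching, landmark HRs ran from 0.72 to 1.39 (TTD) and 0.65 to 1.52 (OS).

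**What to change.** Amend sections 8.2.1, 8.7 and 8.9 and Tables 1 and 4:

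1. Make the main schedule comparison by starting schedule, keeping all starters whatever happens later. Align Table 1, section 8.7 and the Table 4 header on the 2:1 cohort.
2. State that a switch must occur within the first persistent sunitinib episode.
3. For TTD and OS, compare switchers with non-switchers at landmarks (for example 3 and 6 months) among patients still on sunitinib, classified by switch status at the landmark from the change dates already to be coded under section 8.6. A time-dependent model may be added as a sensitivity analysis, with the TTD caveat above and, for OS, with comparators restricted to patients still on sunitinib. State how schedule enters every Cox model.
4. Do not apply or interpret a log-rank test across the three cohorts defined by later events. Label those curves descriptive and not comparable.
5. In section 8.9, name immortal time and say that the landmark analysis addresses it for switches before the landmark. Say that confounding by the reason for switching remains, as does misclassification from assuming 4:2 when the first instruction is missing, and report how many were missing. As an illustration of the latter, with no true switching, 1,000 patients, 20–40% starting on 2:1 and 20–30% of instructions missing, 35–102 patients were coded as switchers, with a TTD HR of 0.84–0.87.

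**Cost.** An amendment, ethics approval under section 9.3, and programming; no new data. Landmarks drop early stoppers (about 700 of 900 remain at 3 months and 550 at 6 under the assumptions above) and ignore later switches. This version is dated 13 April 2021, after the planned report date of 31 March 2021, and the amendment rationale suggests that switch data had already been examined. The landmarks may therefore need a post hoc label.
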